**Table 6. Operating Characteristics**

True % of DLTs	Pr (stopping early)	Median Sample Size (interquartile)
0.10	0.01	30 (30, 30)
0.20	0.10	30 (30, 30)
0.30	0.36	30 (13, 30)
0.40	0.72	13 (5, 30)
0.50	0.94	5 (5, 13)

## 9.0 Reporting Requirements

### 9.1 Treatment periods

Active treatment period is defined from the first day of treatment administration through 30 days after last dose given. The intensity of adverse events (AE) will be assessed according to the Common Terminology Criteria v4.0 (CTCAE). Adverse events and protocol deviations will be reported accordingly to MDACC policy and procedures. Collection of adverse events will reflect the onset and resolution date and maximum grade. Intermittent events should be labeled as such and followed until resolution. If a patient is taken off study while an event is still ongoing, this will be followed until resolution unless another therapy is initiated. Pre-existing medical conditions will be recorded only if an exacerbation occurs during the active treatment period. Co-morbid events will not be scored separately.

### 9.2 Adverse events (toxicities) known to be produced by the transplant chemotherapy regimen:

Gastrointestinal: nausea and vomiting, diarrhea, oral mucositis

Hepatic: self-limited elevations of liver function enzymes; veno-occlusive disease

Pulmonary: acute dyspnea, pulmonary fibrosis and interstitial pneumonitis.

Skin: rash.

### 9.3 Adverse events (toxicities) known to be produced by other treatment components:

The following events are not considered to be significant in relationship with the study treatment, would not be considered adverse events, and will not be collected in the study database.

Myelosuppression-related: neutropenia, anemia thrombocytopenia, platelets and RBCs transfusions.

Flu-like symptoms: low grade fever, headache, chills, cough, rhinitis, myalgia, fatigue, sweating and insomnia.

Mood alteration: depression, anxiety, and agitation

Readmissions (lasting <10 days)

Low blood pressure due to dehydration requiring fluid replacement

Fluid overload.

Fatigue.

Laboratory serum metabolic values not reflecting end-organ (hepatic, renal)

function and or those considered associated to the original disease

Events that are identified to be related to the supportive treatment, e.g., steroids, palifermin, antibiotics.

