## 1.0 Objectives

1.1 Primary: To assess the feasibility of blinatumomab post allogeneic hematopoietic cell transplantation (HCT) as consolidation therapy in patients with B-lineage acute lymphoblastic leukemia (ALL). Toxicities attributable to blinatumomab, acute GVHD, and secondary graft failure will be the parameters to define feasibility.

1.2 Secondary:

1.2.1 To evaluate the progression-free survival (PFS) rate at 1-year for patients with ALL compared to contemporary patient cohort.

1.2.2 To evaluate other efficacy endpoints such as overall survival (OS) and minimal residual disease (MRD) negativity rate in patients treated with blinatumomab for consolidation therapy.

1.2.3 To evaluate, non-relapse mortality (NRM) and chronic GVHD.

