## 2.5 Blinatumomab toxicity profile

The toxicity profile of blinatumomab has been largely consistent with historical studies, with fever, chills, and hypogammaglobulinemia occurring frequently. Tremor, headache, and other mental status changes (e.g., confusion) have been reported. Fever, chills, and other constitutional symptoms are thought to be due to a cytokine release syndrome that occurs shortly after the start of therapy and are reduced with the use of steroids (e.g. dexamethasone 8-24 mg daily x 2-3 days). The adverse effects coincided with a rapid rise in activated T-cells after blinatumomab initiation, essentially confirming the hypothesis (22). Life-threatening neurologic adverse events were uncommon and generally reversible, but seizures have been observed in both the MRD and the active disease studies. Corticosteroids before the first dose and prior to dose escalation ameliorate some of the toxicities.

The adverse reactions in pediatric patients treated with blinatumomab were similar to those seen in adult patients with relapsed or refractory B-cell precursor ALL. Adverse reactions that were observed more frequently in the pediatric population compared to the adult population were pyrexia (80% vs. 61%), hypertension (26% vs. 8%), anemia (41% vs. 24%), infusion-related reaction (49% vs. 34%), thrombocytopenia (34% vs. 21%), leukopenia (24% vs. 11%), and weight gain (17% vs. 6%). In infants and children < 2 years of age, the incidence of neurologic toxicities was not significantly different than for the other age groups, but its manifestations were different (agitation, headache, insomnia, somnolence, and irritability). In the phase I/II open label blinatumomab study in pediatric patients with relapsed / refractory ALL, among the 70 pediatric patients treated on the trial, the most frequent grade 3 adverse events were anemia (36%), thrombocytopenia (21%), and hypokalemia (17%). Three patients (4%) and one patient (1%) had cytokine-release syndrome of grade 3 and 4, respectively. Two patients (3%) interrupted treatment after grade 2 seizures. Reports of compassionate use of blinatumomab in pediatric patients with relapsed / refractory ALL and prior ASCT have shown that blinatumomab did not induce nor exacerbate acute graft versus host disease (24, 25).

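### Section 9.3 leaves non-serious symptoms that Section 2.5 reports with blinatumomab out of the database, with no attribution test, so the descriptive 8.3.4 adverse-event summary would understate drug-related toxicity

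*Combined protocol and SAP*

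**What the plan says.** Section 9.3 is headed as covering toxicities of treatment components other than blinatumomab. Its operative sentence, which concerns the study database, declares the listed items "not considered to be significant in relationship with the study treatment, would not be considered adverse events, and will not be collected". Three lines matter here:

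- the cytopenia line, which reads "Myelosuppression-related: neutropenia, anemia thrombocytopenia, platelets and RBCs transfusions";
- the line on flu-like complaints, which reads "Flu-like symptoms: low grade fever, headache, chills, cough, rhinitis, myalgia, fatigue, sweating and insomnia";
- the line on mood, which reads "Mood alteration: depression, anxiety, and agitation".

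Other lines in the same list name a cause: "Low blood pressure due to dehydration requiring fluid replacement" and "Events that are identified to be related to the supportive treatment, e.g., steroids, palifermin, antibiotics".

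Section 2.5 describes the toxicity of blinatumomab, "with fever, chills, and hypogammaglobulinemia occurring frequently". It links chills to cytokine release, reports headache next to mental status changes, and gives agitation, headache and insomnia among the neurologic manifestations in children under 2. It also gives pediatric and adult rates for anemia and thrombocytopenia.

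Section 1.1 states the feasibility parameters: "Toxicities attributable to blinatumomab, acute GVHD, and secondary graft failure will be the parameters to define feasibility". Section 8.3.4 summarises vital signs, laboratory assessments, adverse events and serious adverse events descriptively. Section 8.3.5 monitors grade 3-4 acute GVHD, secondary graft failure and early non-relapse mortality.

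**The concern.** An adverse-event table can show only what the database holds. Section 9.3 removes terms by name, and several of them are effects that the protocol itself associates with the study drug. Site staff who follow the text would not record a headache or chills during infusion, even when the investigator thinks that blinatumomab caused them.

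What is at stake is the report of non-serious drug-attributable toxicity. Because 8.3.5 counts only GVHD, graft failure and early non-relapse mortality, the 8.3.4 summary is where other toxicity attributable to blinatumomab would appear. An omission there works in one direction only: the drug looks milder than it is.

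**Working it through.** **Step 1. Compare the two lists.** Six terms stand in both 9.3 and 2.5.

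| Term | Line in 9.3 | Cause test on that line | Link in 2.5 | Record outside the adverse-event form |
|---|---|---|---|---|
| Chills | Flu-like | None | Frequent; tied to cytokine release | Only if recorded as CRS |
| Headache | Flu-like | None | Reported generally; also neurologic under age 2 | Only if recorded as a CNS event |
| Insomnia | Flu-like | None | Neurologic, under age 2 only | Only if recorded as a CNS event |
| Agitation | Mood | None | Neurologic, under age 2 only | Only if recorded as a CNS event |
| Anemia | Myelosuppression | None | 41% pediatric, 24% adult | Weekly blood count |
| Thrombocytopenia | Myelosuppression | None | 34% pediatric, 21% adult | Weekly blood count |

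Fever overlaps in part: 9.3 excludes only low-grade fever, and 2.5 does not grade it. It is not counted in the six. Since 4.1 admits patients from age 1, the under-2 wording applies here to ages 1 to under 2.

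**Step 2. Look for a limit on the exclusion.** The heading attributes the events to other treatment components, but the operative sentence excludes everything that follows it. Where a cause was meant to matter, the line says so (dehydration, the original disease, supportive treatment). The three lines above do not. The only severity limit on them is the one attached to fever.

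**Step 3. Look for another route into the data.**

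- 9.4 keeps graft failure, prolonged hospitalization, readmissions over 10 days, and irreversible or fatal events. A non-serious headache meets none of these, and 9.3 excludes shorter readmissions too.
- 9.5 covers serious events and SUSARs.
- Table 4 schedules a physical examination before each cycle and at study completion, not during infusion.
- 5.2 keeps concomitant medications out of the CRF, so symptomatic treatment leaves no trace there.
- Table 4 schedules weekly blood counts in each cycle, so cytopenias can still be shown in the laboratory part of 8.3.4. Their attribution, onset, resolution and maximum grade as adverse events (9.1) are lost.

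What is left unrecorded is isolated, non-serious symptoms related to the drug and not entered as CRS or as a CNS event.

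**Step 4. Check the stopping rule.** Inputs from 8.3.5: prior Beta(0.6, 1.4), toxicity limit 0.30, probability cut-off 0.85. The boundary at n patients is the smallest x with Pr(rate > 0.30 | Beta(0.6 + x, 1.4 + n − x)) > 0.85. For n = 5, x = 2 gives 0.6261 and x = 3 gives 0.8745, so the boundary is 3, as in Table 5. All 25 boundaries from n = 5 to n = 29 match. An exact binomial recursion that checks after every patient from 5 to 29, with a maximum of 30, gives these probabilities of stopping early:

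| True rate | Table 6 | Recomputed |
|---|---|---|
| 0.10 | 0.01 | 0.0103 |
| 0.20 | 0.10 | 0.0966 |
| 0.30 | 0.36 | 0.3576 |
| 0.40 | 0.72 | 0.7184 |
| 0.50 | 0.94 | 0.9384 |

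The rule reproduces. None of its three components is on the 9.3 list, so collecting the listed events would change neither table.

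**Step 5. Try to size the loss.** This would need the rate of each symptom, the share related to the drug, and the share not recorded as CRS or as a CNS event. Section 2.5 gives none of these for chills, headache, insomnia or agitation. No number follows from the documents.

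**Step 6. Compare the wording with 3.3.1 and 7.3.** Both act on grade 4 adverse events, and 3.3.1 expressly includes those defined by laboratory values. Section 9.3 says that cytopenias are not adverse events at all. The passages need to be reconciled.

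**The case against.** The strongest defence is that 9.3 is a deliberate and open choice. Cytopenias and flu-like complaints are hard to attribute after transplant, 4.1 allows entry at an ANC of 0.5 × 10⁹/L and platelets just above 20 × 10⁹/L, and there is no control arm. Section 2.1 describes the cytopenias with blinatumomab as minimal. For cytopenias this largely stands: the weekly counts remain, and whether to enter them as adverse events as well is a fair trade-off.

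A second defence is that a headache judged neurotoxic, or chills judged to be cytokine release, need not be filed under the 9.3 lines and can be recorded as a CNS event or as CRS. That also stands, and it narrows the gap to symptoms recorded as neither. Sections 3.1.3 and 3.1.4 add early inpatient observation and outpatient contact for adverse events. Those provide observation, but they do not put a term that 9.3 excludes into the database. Section 9.1 refers adverse-event reporting to institutional policy, which is not in the documents; 9.3 is nevertheless explicit about the database.

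A reader might be tempted to go further in three ways, none of which the documents support:

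- That drug toxicity could escape the stopping rule because of 9.3. It could not; the rule takes no input from these terms.
- That the loss can be stated as a number of patients out of 30, or that an absent row means zero events. There is no rate for the four symptoms, and a term declared uncollected is not an observed zero. Multiplying the 2.5 cytopenia rates by 30 would not measure the loss either: they are reported rates of events from relapsed or refractory patients, not drug-attributed rates in this population, and cytopenias keep a laboratory record.
- That insomnia and agitation are established drug effects at all ages. Section 2.5 names them only for children under 2.

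**Conclusion.** The point holds within narrow limits. As written, 9.3 keeps isolated non-serious blinatumomab-related symptoms out of the adverse-event part of 8.3.4: chills and headache at any age, and insomnia and agitation on the protocol's own evidence at ages 1 to under 2. That part would understate a parameter named in 1.1 and 8.2. The direction of the bias is clear and its size is unknown. For anemia and thrombocytopenia, only the adverse-event record is lost.

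The consequence is confined to a descriptive safety summary. The formal feasibility decision in 8.2 rests on completing the trial without reaching the stopping rules, and it does not change. The conclusion assumes that sites apply 9.3 literally and that institutional policy does not override it for the study database.

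**What to change.** 1. Add one sentence to 9.3: during the active treatment period defined in 9.1, the exclusion does not apply to a listed symptom that the investigator judges to have at least a possible relation to blinatumomab.
2. For cytopenias, state in 8.3.4 that the worst grade per cycle will be summarised from the blood counts already scheduled in Table 4. Entering them as adverse events can remain optional.
3. Reconcile the statement in 9.3 that listed events are not adverse events with 3.3.1 and 7.3, which act on grade 4 adverse events.

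The cost is protocol wording and some extra CRF entries, with no new procedures. Some recorded symptoms will be hard to attribute in a single-arm study after transplant, so the table should be read with that in mind. With no in-cycle symptom assessment scheduled, the added records will depend on what patients and staff report. The change concerns recording only and proposes no treatment rule.

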#### 9.4 Adverse Events Considered Serious (SAEs):

1. Graft failure/rejection
2. Prolonged hospitalization due to infections and/or organ failure requiring extensive supportive care (i.e. dialysis, mechanical ventilation)
3. Readmissions from any cause resulting in a prolonged hospitalization (>10 days).
4. Any expected or unexpected event resulting in an irreversible condition and/or leading to death.

SAEs will be reported to the PI or his designate, who in turn will notify the IRB following institutional policy.

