#### 9.5 Additional reporting requirements per study sponsor

The sponsor is responsible for compliance with expedited reporting requirements for serious and unexpected and related adverse events (SUSARs), for generation of SAE reports including narratives, and for periodic reporting to Amgen of SAEs

Safety Data	Requirements
Suspected Unexpected Serious Adverse Reaction (SUSARs)	Required (Sent to Amgen at time of regulatory submission)
Serious Adverse Events (SAEs)	Required (Cumulative listing to Amgen every 6 months)
Adverse Events not meeting serious criteria	Not required
Events of Interest	Not required
Pregnancy/Lactation	Required (Sent to Amgen within 10 days of Sponsor awareness)
Event listing for reconciliation	Required at end of study

\*Specific requirements are to be outlined in the ISS Research Agreement

Required Aggregate reports\*:

Safety Data	Timeframe for submission to Amgen

Annual Safety Report            (eg, EU Clinical Trial Directive [CTD] Annual Safety Report, and US IND Annual Report)
	
Annually

Other Aggregate Analyses            (any report containing safety data generated during the course of a study)
	
At time of ISS sponsor submission            to any body governing research conduct (eg, RA, IRB, etc)

Final (End of Study Report), including:
 
 
• Unblinding data for blinded studies
 
• Reports of unauthorized use of a marketed product
 
	
At time of ISS sponsor submission            to any body governing research conduct (eg, RA, IRB, etc) but not later than 1 calendar year of study completion

\*Specific requirements are to be outlined in the ISS Research Agreement

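### Section 9.4 has no life-threatening criterion, so some reversible grade 4 CRS or neurologic events, or repeat seizures, that permanently stop blinatumomab are not classed as SAEs

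*Combined protocol and SAP*

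**What the plan says.** Section 9.4 lists four kinds of serious event:

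1. The first concerns the graft, whether lost or rejected.
2. The second covers long stays, but only for two causes and with a condition on the level of care: "Prolonged hospitalization due to infections and/or organ failure requiring extensive supportive care (i.e. dialysis, mechanical ventilation".
3. The third sets a threshold on length of stay, whatever the reason for coming back: "Readmissions from any cause resulting in a prolonged hospitalization (>10 days".
4. The last turns on how the event ends: "Any expected or unexpected event resulting in an irreversible condition and/or leading to death".

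The list has no life-threatening criterion, no category for medically important events, and no wording that marks it as illustrative.

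Section 9.3 lists events that "would not be considered adverse events, and will not be collected in the study database". One entry is "Readmissions (lasting <10 days", with no condition on cause.

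Section 9.5 requires SAEs to reach the drug supplier as a cumulative listing every 6 months and SUSARs at the time of regulatory submission. The row "Adverse Events not meeting serious criteria" is marked as not required, and so is the row for events of interest. IRB notification of SAEs follows institutional policy (9.4).

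On the drug's known risks, section 2.5 states: "Life-threatening neurologic adverse events were uncommon and generally reversible".

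**The concern.** The SAE definition and the discontinuation rules judge the same events by different standards. The dose-modification section treats a grade 4 CRS, a grade 4 neurologic event or a second seizure as grave enough to end study drug. Section 9.4 asks instead whether the event was irreversible or fatal, or fell under one of three narrower headings. By the plan's own account, life-threatening neurologic events on this drug generally reverse, so the irreversibility test tends to miss the form they usually take.

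At stake is the serious label, and with it the SAE route to the IRB and to the supplier, for toxicities specific to the study drug. The readmission wording adds a second gap: a short readmission caused by the drug is not collected as such, so hospital use from drug toxicity would be under-recorded.

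**Working it through.** The check is mainly a comparison of text, followed by a short calculation of size. The plan gives no figure of its own on this point to reproduce.

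**Step 1. Events that permanently stop the drug.**
- Section 3.3.1: grade 4 events at least possibly related to blinatumomab, with investigator judgement for numerically defined laboratory values.
- Section 3.3.2: grade 4 CNS events, or more than one seizure.
- Table 2: grade 4 CRS, grade 4 neurologic toxicity, more than one seizure, and other clinically relevant grade 4 reactions.
- Section 7 also makes grade 4 events and repeat seizures grounds for removal, when probably or definitely related. The relatedness threshold differs from 3.3.1, and the two passages should be reconciled.

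**Step 2. Take a grade 4 CRS, a grade 4 neurologic event or a second seizure that resolves, and test it against 9.4.**

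| 9.4 criterion | Met? |
|---|---|
| 1. Graft failure or rejection | No, unless it happens as well |
| 2. Prolonged stay for infection or supported organ failure | Only if that support (dialysis or ventilation are the examples) and a prolonged stay occur |
| 3. Readmission over 10 days | Only if the patient had been discharged, came back, and stayed more than 10 days |
| 4. Irreversible or fatal | No, because it resolved |

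An event that meets none of the four permanently stops the drug but is not an SAE.

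**Step 3. Inpatient onset.** Section 2.5 places CRS shortly after the start of therapy, and 3.1.3 recommends hospitalisation for at least the first 3 days of the first cycle. An event during that stay is not a readmission, so criterion 3 does not apply at any length of stay. Only criterion 2 could capture it if it resolves without graft failure.

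**Step 4. The readmission thresholds.**
- Under 10 days: excluded from collection by 9.3.
- Over 10 days: serious under 9.4.
- Exactly 10 days: in neither section.

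**Step 5. Size.** Inputs: 1 grade 4 CRS among 70 patients in the cited paediatric relapsed/refractory study (2.5), and a maximum of 30 patients (Tables 5 and 6).
- Rate: 1/70 = 1.4%.
- Expected number: 30 × 1/70 = 0.43, about 0.4 patients.
- Chance of at least one: 1 − (69/70)^30 = 1 − 0.649 = 0.351, about 35%.

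One event in 70 is imprecise. The exact (Clopper-Pearson) 95% interval for the rate runs from 0.04% (the 2.5th percentile of a beta(1, 70) distribution) to 7.7% (the 97.5th percentile of a beta(2, 69)). Multiplied by 30, that is about 0.01 to 2.3 patients. The interval reflects sampling error only, not the difference between populations.

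The documents give no usable rate for grade 4 neurologic events or repeat seizures, so those cannot be added to the figure.

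**The case against.** Several points on the other side stand.

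**The events are not lost.** Grade 4 CRS and seizures are not among the 9.3 exclusions. Section 9.1 has adverse events collected with onset, resolution and maximum grade, and reported under institutional policy; 8.3.4 summarises them. The supplier also receives annual, other aggregate and final reports (9.5). A reader might infer that the drug's main toxicities go unreported. The documents do not support that: the loss is of serious classification and its route and timing.

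**Criterion 2 catches some of these events.** It has no day threshold and does not require irreversibility, so a patient ventilated for CRS could meet it. It is therefore wrong to say that every reversible event with discharge by day 10 escapes.

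**The effect on SUSAR reporting is not shown.** A reader might infer that expedited reports depend on the 9.4 list. Section 9.5 makes the sponsor responsible for expedited reporting requirements without tying seriousness there to 9.4, and refers specifics to a research agreement. Neither that agreement nor institutional policy is in the documents, and either may use a wider definition. A SUSAR must also be unexpected, and 2.5 already describes CRS and seizures.

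**The primary decision is unaffected.** A reader might link the gap to the feasibility objective. Section 8.2 defines success as finishing without reaching the stopping rules, and 8.3.5 counts grade 3-4 acute GVHD, secondary graft failure and early NRM. None of these depends on the SAE label.

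**A larger count is tempting but does not match the claim.** Pooling grade 3 and 4 CRS gives 4/70 = 5.7%, or 1.7 of 30 patients. Grade 3 CRS by itself leads to interruption and restart, with a permanent stop only if it is prolonged. The two patients with seizures in that study had grade 2 events and interrupted treatment.

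What remains is the mismatch in the protocol's own text. A wider definition elsewhere would be a reason to align 9.4 with it, not to leave 9.4 narrower.

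**Conclusion.** The point holds as a gap in serious classification. As 9.4 is written, a reversible grade 4 CRS, grade 4 neurologic event or repeat seizure can permanently stop blinatumomab without being an SAE. Readmissions under 10 days are uncollected even when the drug is the cause, and a 10-day stay belongs to neither list.

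The expected number is small: about 0.4 grade 4 CRS events in 30 patients, with about a 35% chance of at least one. This is an upper figure for CRS events that would be missed, since some would meet criterion 2 or another criterion. It assumes that the rate in children with relapsed or refractory disease and more than 25% marrow blasts carries over to patients aged 1-70 in remission or with MRD; the documents neither support nor refute that.

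The conclusion also rests on reading 9.4 as a complete list, which is the natural reading of its text. It does not extend to non-collection of the events themselves, to a demonstrated failure of SUSAR reporting, or to any change in the primary feasibility decision. The change is worth making because each such event matters in a trial of 30 patients and the remedy is cheap.

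**What to change.** - In 9.4, add any life-threatening event, naming grade 4 CRS and grade 4 neurologic events, whether or not it reverses. A repeat seizure below grade 4 might not meet that wording, so the sponsor should state explicitly whether it counts.
- In 9.3, state that the exclusion of short readmissions does not apply when the cause is at least possibly related to blinatumomab.
- Align the thresholds in 9.3 and 9.4 so that a stay of exactly 10 days is covered, for example by making the 9.4 criterion 10 days or more.
- Check the revised definition against institutional policy and the research agreement so that all use the same one.

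The cost is a wording amendment and a few more SAE reports. The change affects reporting only; dosing, interruption and discontinuation rules stay as they are.
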